Addressing tobacco and other substance use simultaneously can lead to better outcomes than addressing each substance separately. Smoking cessation interventions delivered in the context of alcohol or drug treatment do not impede recovery,⁶⁸ and may actually reduce alcohol and other substance use with adults^{69–71} as well as teens.^{72–74} School-based prevention interventions such as those based on the Transtheoretical Model of Change⁷⁵ and Project Towards No Drug Abuse⁷⁶ have demonstrated that targeted multiple substances simultaneously can have positive outcomes. As directly applied to tobacco use and heavy drinking, Toll et al. showed that in adults who use tobacco and drink heavily, adding an alcohol component to tobacco quitline counseling resulted in significantly greater tobacco abstinence at 7 month follow-up (13.5%) compared to tobacco counseling alone (10.3%).⁷⁷ For young adults, Ames and colleagues showed that integrated treatment addressing both risk behaviors would be acceptable to young adults and, compared to standard tobacco treatment, resulted in more participants biochemically confirmed abstinent from tobacco at 3 month follow-up (but no differences in drinking outcomes between groups).⁷⁸ A subsequent pilot trial showed that participants who received integrated intervention were more likely to have biochemically confirmed abstinence from tobacco, consumed fewer drinks per month ($p < 0.05$) and had fewer binge drinking episodes per month ($p < 0.05$) than those who received standard treatment at 6 months follow-up.⁷⁹ **Thus, there is potential for an integrated intervention to result in better tobacco and alcohol outcomes for young adults than treating tobacco alone. Extending an integrated intervention to a digital environment could maximize reach and utility for young adults.**

To our knowledge only one previous study has tested the effectiveness of a digital health intervention jointly targeting smoking and HED in young adults.⁸⁰ Compared to a minimal assessment control condition, a 14-day mobile feedback intervention based on the BASICS curriculum resulted in a decrease in the number of cigarettes smoked, but did not reduce HED or concurrent smoking and drinking at the 1 month follow-up. There were no significant differences between the mobile BASICS intervention and a mobile assessment control condition. **More research is needed to determine how best to harness digital tools to target tobacco use and HED in young adults.**

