While preliminary work is not necessary for a Planning Grant application (R34), our team has pilot data and expertise that is directly relevant to this application.

Development, feasibility and efficacy of the Tobacco Status Project (TSP). During her postdoctoral fellowship, [name] led a mixed-methods study to determine how young adult smokers would like to use Facebook to help change smoking behavior. About a third (31%) of survey respondents reported they would want to quit smoking using Facebook, and interest was greater among those more motivated to quit, who had made a quit attempt in the past year, and had previously used the Internet for assistance with a quit attempt (all $p<0.01$). In qualitative interviews, social support and convenience were identified as strengths of a Facebook intervention, while privacy was the main concern.⁴

[name] is currently funded with a five-year K23 career development award from NIDA to develop and test the feasibility and efficacy of Tobacco Status Project, combining Facebook contacts tailored to participants' readiness to quit smoking with a 12-week cessation program consisting of 7 state-of-the-art group cognitive-behavioral sessions occurring over Facebook text chat. A feasibility trial enrolled 79 young adults who formed 7 Facebook groups. Follow-up rates were 84% and 72% at 6 and 12 months, respectively, and reported 7-day abstinence was 21% at 6 months (9% biochemically-verified) and 18% at 12 months (9% verified).^{6,7} From baseline to 12-months, there was a significant increase in the proportion prepared to quit (13% to 46%, $p<.001$), 35% reduced their cigarette consumption by 50% or greater, and 67% reported a 24-hr quit attempt. Engagement in the intervention was high, with 92% participation in the full 3 month intervention and 61% commented on at least one post, with more commenting among those randomized to receive a personal monetary incentive.¹⁰⁹ Participants reported reading most of the Facebook posts (mean usability rating=3.3/4) and interactions from counseling sessions (3/4), thinking about what they read (3/4) and would recommend the program to others (3.3/4). Given low participation in CBT sessions (7 of 79 participated) but extremely high engagement (6/7 sessions attended on average) we incorporated the sessions directly into the Facebook groups for a larger efficacy trial currently underway.

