In a 3-year controlled trial, we are randomizing 480 young adult participants to either TSP or referral to the National Cancer Institute Smokefree.gov website (control). In 34 weeks, we have randomized 309 young adult smokers, consistent with the proposed timeline, 19% were ready to quit smoking in the next 30 days, and the TSP group has 19 groups actively running or completed. Among TSP participants in groups that have completed the 3-month intervention (n=66), 73% commented at least once to their Facebook group. At 3 month follow-up (treatment end), follow-up rate is 71%, biochemically-verified 7-day point prevalence abstinence among completed cases is 7.1% in the TSP group and 0% in the control group. A majority of participants in both groups reported a 24 hour quit attempt during the 3-month intervention period (62% TSP; 60% control). More participants in the TSP group reported intention to quit smoking in the next 30 days (43%) than those in the control group (35%). At baseline 68% of the sample drank alcohol in the past month and 51% of all drinkers reported current HED. Although promising, there is a need to determine whether expanding the intervention to address multiple substance use will yield maximal effectiveness. **This pilot work will directly inform the present study.**

Facebook Recruitment. Drs. [name] and [name]'s research has previously found social media to be an efficient and affordable source of recruitment for young adult smokers. A survey study (N=1987) reported a cost of \$4.28 per valid completed online survey, far more affordable and targeted than other online recruitment methods.¹¹⁰ The TSP feasibility trial, discussed above, reported a cost of \$8.80 per eligible consented young adult smoker into our Facebook intervention.¹¹¹ Gender and ethnicity have differed by online recruitment source in our work (e.g., Craigslist, Facebook, survey sampling), suggesting the utility of combining recruitment methods.¹¹² **Our experience with social media recruitment will inform recruitment in the present study.**

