Summary. Numerous studies, including ours, have shown high rates of tobacco and alcohol co-use among young adults; yet this population is less likely to present for formal treatment than those of other age groups. Our group has demonstrated that we have the capability to recruit young adults throughout United States using online strategies, collect biochemical verification of tobacco abstinence, and retain participants in our longitudinal studies. Our Tobacco Status Project Facebook intervention shows great promise for helping young adults quit smoking. The next essential step in this line of research is to subject this intervention to a more rigorous test of efficacy and determine whether multiple substances should be targeted for maximum effectiveness.

C.3. Overview of Design

The proposed 3-year research plan will target young adults who smoke cigarettes and also have HED in two phases (**Fig. 1**).

Phase I consists of formative work to adapt the existing Tobacco Status Project Intervention (TSP) to include a component targeting alcohol (TSP+ALC) and will also conduct online usability testing with the target population. **Phase II** is a pilot randomized trial (N=160) testing the efficacy of

TSP+ALC compared to TSP on smoking and drinking outcomes. Participants will be young adults who have smoked 100+ cigarettes in their lifetimes and smoke at least 4 days per week on average, have had at least one heavy drinking episode in the past month (5+ for men, 4+ for women), and use Facebook on 4+ days per week. Primary outcome will be biochemically verified 7-day abstinence from smoking. Secondary outcomes will be days of HED, sum of days using either tobacco or alcohol in the past 30 days, and dependence symptoms, quit attempts, motivation, and thoughts about tobacco and HED abstinence.

C.4 Formative work: Focus groups

Focus groups will be used to inform the design of a Facebook intervention targeting tobacco use and HED among young adults (TSP+ALC). During this Phase, investigators will seek consultation services from **[name]** through the UCSF Clinical and Translational Sciences Institute Study Design Consultation Service, to help develop qualitative interview questions and conduct data analysis.

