Sample size and power analysis. The sample N of 160 was set primarily for practical and clinical reasons and not driven by estimated effect sizes or hypothesis testing. We expect to have representation (although not equal) among males and females, and across ethnic groups consistent with our current trial of TSP. We also expect to have representation across levels of smoking and drinking, and readiness to quit using both substances. We anticipate an attrition rate of 30% at 3, 6, and 12 months, yielding a final sample size of 112 (56 in each group), enabling us to compare groups on primary and secondary outcomes at each timepoint. This will also generate an effect size estimate that will be useful for powering a larger trial.

A goal of 6 participants will be recruited per week during the 6-month recruitment period, which is in line with recruitment for our feasibility trial and current RCT.¹¹¹

Procedures. Participants will be recruited through Facebook and Craigslist advertisements, using a similar strategy to that of focus group and usability-testing. All advertisements will provide a link to the study’s website, with eligibility questions. If respondents are eligible, then they will be taken to the informed consent webpage. Participants consenting to participate in the study will be asked to verify age by sending proof through email or social media, a process used successfully in [name] previous research. Verified participants will be emailed a baseline assessment. Those completing the baseline assessment will be randomized to either TSP, or TSP+ALC, stratified based on readiness to quit smoking (Ready in the next 30 days, Not Ready in 30 days) and smoking pattern (daily vs. non-daily), variables known to be related to outcomes and addressed by the intervention.¹⁶¹ A stratified random assignment program will be developed in consultation with [name], and used currently in [name] RCT of TSP. All participants will then be assigned to a secret group tailored to their condition and readiness to quit tobacco. Groups will begin when there are approximately 12 participants enrolled, as that has been deemed the optimal number based on analyses of engagement in our previous work.^{109, 162} Groups will receive one social media post daily for 90 days and weekly “The [name] In” counseling sessions managed

[figure not shown]

Figure 2. Participant flow through the study

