6. Data cleaning, data analysis, manuscript submission Aim 3 (FB data)																		
7. Data cleaning, data analysis, manuscript submission Aim 3 (pilot trial)																		
8. Prepare and submit R01 application for RCT																		

C.13. Future Plans

The proposed Project fits within the research team's program of research focused on using social media to reduce substance use. Based on the results of the pilot randomized trial to be conducted here, anticipated next steps include submission of an application for a randomized controlled trial powered to detect differences across groups in both tobacco and alcohol outcomes.

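### The pilot's treatment effect on verified abstinence would be too imprecise to size the larger trial, contrary to what the sample-size section says

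*Combined protocol and SAP*

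**What the plan says.** Section C.8, under Sample size and power analysis, is open about where the number came from: "The sample N of 160 was set primarily for practical and clinical reasons and not driven by estimated effect sizes or hypothesis testing". It expects 30% attrition, leaving 112 participants, 56 per group, for comparison on primary and secondary outcomes. The paragraph then closes with the claim at issue: "This will also generate an effect size estimate that will be useful for powering a larger trial". It gives no interval width, no smallest effect of interest and no caution about the point estimate.

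The overview of the design (C.3) states: "Primary outcome will be biochemically verified 7-day abstinence from smoking".

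Two later sections bear on how the result would be used. C.11 (Choice of control condition) ties a further grant application to TSP+ALC giving better tobacco or alcohol outcomes than TSP, and says that trial would use a control closer to standard treatment, for example a website referral. C.13 describes the next step, based on the pilot's results, as "submission of an application for a randomized controlled trial powered to detect differences across groups in both tobacco and alcohol outcomes".

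**The concern.** Saying that an effect estimate will help to power a trial implies that it is precise enough to separate the effects that would lead to different trial sizes. With a rare binary outcome and 56 per arm, it may not be. A pilot that happens to overestimate the effect leads to an underpowered successor. One that happens to show nothing, or a reversal, may end a useful programme. The plan's readers, including those who will judge the next application, would take from this sentence an assurance that the design may be unable to give.

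**Working it through.** **The plan's own figure.** 160 × (1 − 0.30) = 112, or 56 per arm. This reproduces. The plan states no power, alpha or target effect, so there is nothing further to reproduce.

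**Inputs.**
- TSP verified abstinence at 3 months, from the trial now running: "biochemically-verified 7-day point prevalence abstinence among completed cases is 7.1% in the TSP group and 0% in the control group".
- TSP verified abstinence in the feasibility trial: 9% at 6 months and 9% at 12 months (preliminary work).
- Adding an alcohol component to tobacco counselling: 13.5% versus 10.3% at 7 months, from the adult quitline study cited in section A. This is the only pair of abstinence rates in the document for that contrast.
- Assumed, because not stated: two-sided alpha 0.05, 80% power, equal allocation, no clustering. The TSP+ALC rate is unknown; 13.5% is borrowed from the quitline study.

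**Expected quitters per arm.** 56 × 0.071 = 4.0; 56 × 0.09 = 5.0; 56 × 0.103 = 5.8; 56 × 0.135 = 7.6. So about 4 to 8.

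**Precision at 4/56 versus 8/56.**
- OR = (8 × 52)/(4 × 48) = 2.17.
- SE(log OR) = √(1/4 + 1/8 + 1/52 + 1/48) = 0.644.
- 95% CI = exp(0.773 ± 1.96 × 0.644) = 0.61 to 7.66.
- Risk difference 7.1 points, Wald 95% CI −4.2 to 18.5 (Newcombe −4.8 to 19.4).

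The interval includes a halving of the odds less a little, no effect, and a more than sevenfold increase.

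**Size the next trial would need for this contrast.** n per arm = [1.96√(2p̄(1−p̄)) + 0.842√(p₁(1−p₁) + p₂(1−p₂))]² / (p₂−p₁)², with p̄ the mean of the two rates.
- 7.1% versus 13.5%: p̄ = 0.103, difference 0.064, n = 353.
- 10.3% versus 13.5%: p̄ = 0.119, difference 0.032, n = 1,606.

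**What sizing from the pilot would produce.** For every possible pair of quitter counts, the binomial probability was computed, the observed rates were put into the same formula, and the resulting n was compared with the true need. Pilots with no advantage for TSP+ALC give no usable n.

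| True rates | Analysed per arm | Under half the need | No advantage | Within a factor of two |
|---|---|---|---|---|
| 7.1% vs 13.5% | 56 | 34% | 17% | 30% |
| 10.3% vs 13.5% | 56 | 42% | 35% | 12% |
| 7.1% vs 13.5% | 80 | 30% | 11% | 36% |
| 10.3% vs 13.5% | 80 | 41% | 31% | 19% |

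The remainder in each row is pilots that give more than twice the need. The 35% is about 25% in the wrong direction plus 10% exact ties. The rows for 80 per arm treat everyone randomised as observed, which is the most that the multiple imputation planned in C.9 could recover.

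**Continuous outcomes.** With 56 per arm, the 95% CI for a standardised difference is about ±1.96 × √(2/56) = ±0.37 SD.

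**Clustering.** C.5 expects about 16 Facebook groups of about 10, 8 per arm. For an assumed intracluster correlation of 0.01 to 0.05, the design effect 1 + (10 − 1) × ICC is 1.09 to 1.45. The figures above ignore this and so are somewhat optimistic.

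**The case against.** The strongest reply is that the plan claims little. It says outright that N was pragmatic, and it nowhere says that the next trial will be sized on the point estimate alone. A reader might infer such a commitment, but the document does not contain one: C.13 lists only anticipated next steps and gives no sizing method. That stands. The fault is that the sentence claims a usefulness the design lacks for the primary outcome, and sets no limit on how the estimate will be used.

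Second, the sentence names no outcome, and heavy-drinking days or drinks per week are estimated better. This also stands in part. However, the sentence follows one that covers primary and secondary outcomes, and ±0.37 SD is still weak for choosing a sample size.

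Third, the size of the problem depends on the assumed truth. A reader might conclude that the next trial would most likely be far too small or be abandoned. Under 7.1% versus 13.5% the two outcomes together come to about 51%, an even chance; only under 10.3% versus 13.5% do they reach about 77%. The documents do not settle which is closer, and the 13.5% comes from adult quitline callers, not young adults on Facebook.

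Fourth, imputation and repeated assessments add information. They add some, but the gain from 56 to 80 per arm is modest, and abstinence at 3, 6 and 12 months comes largely from the same few people.

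None of this is an argument against 160 participants for a feasibility pilot. Retention, for example, is estimated tolerably well: 48/160 gives a 95% CI of about 23% to 38%.

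**Conclusion.** The point holds for the primary outcome. With about 4 to 8 verified quitters expected per arm, sizing the next trial from the point estimate would land within a factor of two of the true need in only about 30% of pilots (7.1% versus 13.5%) or 12% (10.3% versus 13.5%). With all 80 per arm analysed, this rises only to 36% and 19%.

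There is a separate reason that does not depend on precision. The pilot estimates TSP+ALC against TSP, while C.11 expects the larger trial to compare TSP+ALC with something like a website referral. Even a precise pilot effect would not transfer directly.

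The conclusion rests on the team's earlier TSP rates carrying over, on 13.5% as a stand-in for TSP+ALC, and on the assumed alpha and power. It concerns one sentence about use of the estimate. It is not a finding that N = 160 is wrong, that the plan has committed to a flawed sizing rule, or that failure of the next trial is probable whatever the true rates.

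**What to change.** Replace the closing sentence of the sample-size paragraph in C.8 with text that says three things:

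1. The treatment effect will be reported with its 95% CI, and its point estimate will not be used to size the next trial.
2. The pilot will supply, each with a 95% CI, the TSP verified abstinence rate, retention, completion of cotinine verification, and the SD of heavy-drinking days. Any within-group correlation from about 16 groups should be described as a rough guide only, since it too will be very imprecise.
3. The larger trial will be powered on a pre-stated smallest worthwhile difference against its own comparator.

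Retention and verification completion are already planned outputs in C.8 and C.9, so part of this only needs a cross-reference. C.13 should be read alongside, so that its reference to the pilot results does not restore the claim.

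The cost is wording only. Sample size, conduct, endpoints and analysis are unchanged. The price is a less favourable statement of what the pilot will deliver.

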We will offer a free 14-day starter pack of nicotine patch to all participants regardless of intervention condition, given findings that smokers receiving a 14-day starter pack showed more satisfaction with a telephone quit line and had higher 7-day quit rates compared to those not receiving patch.⁹⁶ In our current trial, at baseline, 88% were daily smokers and participants averaged 11.8 (SD=14.3) cigarettes per day and 2.8 years (SD=.6) of smoking; the sample averaged low to moderate nicotine dependence (FTND score=3.0, SD=1.6) It is anticipated, therefore, that NRT will be necessary and useful for many participants. For those who are not nicotine dependent, we do not anticipate any decrease in the probability of quitting due to nicotine patch availability.^{156, 157} Further, NRT use will not be required for study participation. All participants who smoke an average of 5 or more cigarettes per day in the past 30 days and who are still members of a Facebook secret group at the time the group starts will be offered the nicotine patch. The 5 cigarettes per day criterion is based on successful implementation in [name] trial with depressed outpatient smokers¹⁵⁸ and trials

with adolescents and smokers in inpatient psychiatry led by [name] (Co-Investigator).^{100, 159} At any time during the three month intervention, participants will be mailed nicotine 21-mg, 14-mg, or 7-mg patches based on smoking rate at intake. Participants in both conditions will be encouraged to discuss use and ask questions during weekly counseling sessions.

C.6 Usability testing

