through the study's private group pages. If participants wish to have private study interactions with study staff they can do so at any time. Three-month follow-up assessments will be emailed to participants upon completion of treatment.

Informed consent, baseline and 3, 6, and 12 month assessments will be delivered using the online survey program Qualtrics, which is HIPAA-compliant, has been used often in medical research, and is being used successfully by [name] for her current Facebook intervention study. Verification of non-smoking status will be conducted for all participants reporting no smoking in the past 7 days at the post-test assessment using mailed saliva cotinine test kits and verified online as described in the **Measures** section. Participants will receive their choice of Amazon or Best Buy gift cards in the amount of \$20 for each 20-30 minute online survey, and a bonus \$20 for completing all assessments, for a total of \$100 possible compensation for participation. Amazon and Best Buy were chosen as retail outlets given their overwhelming popularity among a large choice of retailers given in [name] previous studies with young adult smokers.^{4, 111} Assessments will not be considered complete until staff receives verification of abstinence.

Measures.

Primary outcome (tobacco):

- **Biochemically-verified 7-day point prevalence abstinence from all tobacco products** will be assessed at 3, 6, and 12 months. Participants reporting no smoking in the past 7 days will be coded as abstinent from cigarettes. Those reporting 7-day abstinence will be mailed a saliva cotinine test kit, and record two pictures: one giving a saliva sample, and another of the test result. Participants with a salivary cotinine level <11 ng/ml, indicating nonsmoking,¹⁶³ will be considered confirmed nonsmokers. Biochemical verification is recommended in randomized trials with sample sizes under 500,¹⁶⁴ saliva cotinine test kits have been successfully mailed to participants in previous studies,¹⁶⁵ and [name] is using this method successfully in her K23 Facebook smoking cessation RCT with young adults (to date, 50% reporting 7-day abstinence have successfully completed biochemical verification). If participants indicate use of an electronic nicotine delivery-system to aid in smoking cessation, saliva cotinine and reported ENDS use will be recorded and reported separately from biochemically verified abstinence.

Secondary outcomes (tobacco):

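### The cotinine rule for verified abstinence makes no provision for the nicotine patch the trial supplies; secondarily, the completeness sentence should be confined to payment

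*Combined protocol and SAP*

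**What the plan says.** **Outcome.** C.8, Measures, names the primary outcome as biochemically verified 7-day abstinence from all tobacco products at 3, 6 and 12 months. Self-report comes first: "Participants reporting no smoking in the past 7 days will be coded as abstinent from cigarettes". Those people are mailed a saliva kit, and the confirmed nonsmokers are "Participants with a salivary cotinine level <11 ng/ml, indicating nonsmoking". One nicotine source is treated separately: "If participants indicate use of an electronic nicotine delivery-system to aid in smoking cessation", then "saliva cotinine and reported ENDS use will be recorded and reported separately from biochemically verified abstinence".

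**Patch.** C.5, Nicotine Replacement Therapy, states: "We will offer a free 14-day starter pack of nicotine patch to all participants regardless of intervention condition". The same paragraph narrows the offer to those averaging 5 or more cigarettes per day who are still group members when the group starts. Patches may be mailed at any point in the three-month intervention. Under C.8, Procedures, the 3-month survey goes out when treatment ends.

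**Completeness.** The paragraph on gift cards in C.8, Procedures, ends: "Assessments will not be considered complete until staff receives verification of abstinence". C.8, Feasibility Measures, defines retention by who completes the assessments, and item (4) of the C.9 feasibility analysis defines attrition the same way. Item (3) separately tracks, at 3 months, the share of reported quitters who complete a cotinine test and the discordance between cotinine and self-report. The C.9 primary model describes the outcome as 7-day point prevalence, without repeating that it is verified, and handles missing data by multiple imputation. On verification in the current trial, C.8 reports: "50% reporting 7-day abstinence have successfully completed biochemical verification".

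**The concern.** **Patch (main point).** Patch is nicotine but not tobacco, so someone can meet the named outcome while using it. The ENDS provision shows that the plan recognises nicotine from a source other than cigarettes as a problem for cotinine. It makes no such provision for the one product the trial hands out. A tobacco-abstinent patch user tested at 3 months can therefore fail the cut-off, be counted as not verified, and also appear in item (3) as a discordant self-report. That would make a feasibility result about honest reporting partly a measure of patch use.

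**Completeness (secondary point).** If the payment-paragraph sentence carries over to retention, attrition and imputation, a reported smoker is complete on submitting the survey, while a reported quitter with no result is not. Missingness would then depend on reported quitting, which is close to the outcome itself.

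The stake is the primary outcome of a pilot with few expected events, whose effect size estimate is meant to help power a larger trial (C.8, Sample size).

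**Working it through.** **Plan's own figure.** 160 × (1 − 0.30) = 112, or 56 per arm. This agrees with C.8.

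**Patch.** The preliminary-work section on the current trial says "biochemically-verified 7-day point prevalence abstinence among completed cases is 7.1% in the TSP group" at 3 months. Taking that as the rate that would be verified without interference from patch: 56 × 0.071 = 3.98 quitters per arm.

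Assumptions, none of them given in the documents: every one of these quitters takes the pack, uses it for 14 consecutive days, and has cotinine at or above 11 ng/ml while on it and not afterwards. The number on patch at the test is then 3.98 × (overlapping days ÷ length of the start window).

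| When packs are started | Tested day 90 | Tested day 97 | Tested day 104 |
|---|---|---|---|
| All with the group | 0 | 0 | 0 |
| Evenly over 90 days | 3.98 × 14/90 = 0.62 | 3.98 × 7/90 = 0.31 | 0 |
| All in the last 30 days | 3.98 × 14/30 = 1.86 | 3.98 × 7/30 = 0.93 | 0 |

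On day 90 the verified rate would read (3.98 − 0.62)/56 = 6.0% or (3.98 − 1.86)/56 = 3.8%, against 7.1%. Incomplete uptake lowers the effect, and NRT from other sources adds to it. At 6 and 12 months a 14-day pack mailed within the first 3 months should rarely matter.

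**Completeness.** Compare coding reported quitters with no result as not verified against dropping them. First suppose every unverified quitter returned nothing, which gives the largest gap.

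- Current trial (7.1% verified, 50% of reported quitters verified, so 7.1% unverified): 0.071/(1 − 0.071) = 7.6% against 7.1%, a gap of 0.5 point. Standard error with 112: √(0.071 × 0.929/112) = 2.4 points.
- Feasibility trial, 6 months (21% reported, 9% verified): 0.09/(1 − 0.12) = 10.2% against 9.0%, a gap of 1.2 points.
- Feasibility trial, 12 months (18% reported, 9% verified): 0.09/(1 − 0.09) = 9.9% against 9.0%, a gap of 0.9 point.
- Mixed case (21% reported, 50% verified): 112 × 0.21 = 23.52 reported, 11.76 verified, 11.76 unverified. 11.76/112 = 10.5%; 11.76/(112 − 11.76) = 11.7%, a gap of 1.2 points. Standard error: √(0.105 × 0.895/112) = 2.9 points.

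If instead half of the unverified in the mixed case returned a failing test, only 5.88 have no result: 11.76/(112 − 5.88) = 11.1%, a gap of 0.6 point. The split between no return and failed test is not in the documents.

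On the same largest-gap assumption, measured retention would fall from 112/160 = 70% to (112 − 7.95)/160 = 65% at the current trial's rates, or (112 − 11.76)/160 = about 63% in the mixed case.

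**The case against.** **On patch.** Supply is one 14-day pack, the survey follows the end of treatment, and the kit is mailed only after abstinence is reported, so overlap may be nil. The documents give no cotinine level for patch users, and the follow-up smoking questionnaire is not itemised, so NRT use may already be collected. All of this stands and limits the size. It does not remove the gap in the rule: no text uses such an answer to classify the outcome, and mailing records alone do not show use at sampling.

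**On completeness.** The sentence closes a paragraph about gift cards. Read word for word, it would leave reported smokers incomplete as well, which cannot be intended. The outcome's name makes a non-returner not verified, and items (3) and (4) of the C.9 feasibility analysis separate test completion from attrition. These arguments are strong, and payment is the likelier meaning. What remains is that the plan does not say so and states no code for an untested quitter.

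**Stronger readings not supported.**
- A reader might infer bias between arms. Patch and kits are offered alike in both, and nothing indicates that use or return differs by arm.
- A reader might take the completed-cases denominator in the current trial as evidence that completion was defined there by verification. That figure follows a 71% follow-up rate, and nothing ties it to cotinine.
- A reader might infer a large inflation from imputation. Neither the imputation model nor the split between failed and unreturned tests is given, so no figure can be defended.

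**Conclusion.** The patch point holds as a gap in the outcome rule. Its size is unknown and may be zero: 0 to about 2 of roughly 4 quitters per arm, mainly at month 3, under full uptake, testing on day 90, and patch lifting cotinine over the cut-off. With so few expected events, one or two people matter to the estimate and to the discordance measure.

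The completeness point holds only as an ambiguity. It has no effect if the sentence concerns payment. If it reaches the analysis, the verified rate shifts by about 0.5 to 1.2 points at most compared with dropping non-returners, within one standard error, and less if some of the unverified returned failing tests. Measured retention would move by more, about 5 to 7 points if all of the unverified returned nothing. It would be wrong to say that the plan will treat untested quitters as missing; the text permits that reading but does not require it.

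Both should be settled before outcome data are seen. Neither threatens the design.

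**What to change.** **Patch.** At each follow-up, ask about NRT use in the past 7 days alongside the ENDS question. Report cotinine for NRT users separately and leave them out of the discordance count. The main analysis can keep the cut-off as written. Add one sensitivity analysis that counts self-reported quitters on NRT as abstinent.

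**Completeness.** State that the verification sentence governs payment only. Define completion for retention, attrition and missing data as survey submitted. In the primary model, code a reported quitter with no cotinine result as not verified-abstinent, and impute only when the survey itself is missing.

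**Cost.** One survey item and a few sentences of analysis text, with no new procedure. The downsides are one more reporting category and a verified rate slightly lower than dropping non-returners would give.
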